School-based HPVV can improve participation (10) and coverage among children of all ethnicities (11). Studies have shown positive attitudes towards counselling supporting school-based vaccination (12), but to increase the attendance of ethnic minority children, communication needs to follow examined guidelines regarding communicating with ethnic minority citizens concerning health issues (13, 14). Communication needs to be uniform, simple, and in ethnic minority languages. The environment must be trustworthy and reliable, and the information is best adopted if visual, with an opportunity for repetition (15).

Hypotheses and aims

Hypothesis 1: It is possible to improve participation in HPVV in DK when combining HPV-counselling with school-based vaccination compared to GP-based vaccination.

- Aim 1: To improve HPVV coverage among pupils attending schools with high concentration of non-native pupils. We anticipate improving HPVV among ethnic minority pupils with at least 10%-point, and among native Danish pupils with at least 5%-point.

Hypothesis 2: It is possible to improve participation in HPVV among siblings to enrolled pupils, solely by improving HPV knowledge and awareness among their parents.

- Aim 2: To improve HPVV coverage among siblings to enrolled pupils.

Hypothesis 3: A close cooperation with user-representatives will improve feasibility and implementation.

- Aim 3: To develop and evaluate targeted counselling material concerning HPV and HPVV for parents and children with various ethnical backgrounds, eligible for national implementation.

Materials and methods

Theoretical framework

The intervention is developed according to Complex Interventions Framework (16, 17). Complex interventions contain several interacting components, and the guideline deals with development, assessment of feasibility, implementation, and evaluation (Figure 1). To operationalize the elements of the intervention, we have applied a Logic Model, a graphic tool that illustrates the relationship between activities and intended outcome (18, 19). By this, we have combined theoretical knowledge and components of the intervention to accommodate to possible challenges in implementation (Table 1).

Research design, study and control population

First vaccination (HPVV1) will be offered after element 1-2 have been completed; the second (HPVV2) will be offered minimum five months later. Both will be given at pre-defined dates during school hours by qualified doctors and nurses. Dates will be visible on posters at school and reminder will be sent to parents via AULA and text messages if this is selected by parents when submitting their child for vaccination.

Evaluation plan

Quantitative outcome

Primary: HPVV coverage between intervention and control group as a total and stratified by ethnicity.
Secondary: HPVV coverage for siblings of included pupils compared to an age- and area matched control group.

Qualitative evaluation

Parents' and school professionals' perceptions of the intervention will be qualitatively evaluated by focus-group interviews. The participants will be strategically selected among attending and non-attending, and represent various schools, cultural and socio-economic conditions. The interviews will be framed by a semi-structured interview guide, and data will be analysed and validated consecutively with Malterud's text analytical method (22).

Power calculation

We have enrolled 5 schools, corresponding to approximately 640 children. 2560 children will be allocated to the control group (1:4 ratio). In both groups, roughly half of these children will be native Danes and the other half will be ethnic minorities. Estimating that minority pupils have a HPVV coverage of 65%, the study will be able to detect a difference of approximately 10 percent points in vaccination coverage between intervention and control group in the stratified analyses with a risk of type 1 error of 5% and type 2 error of 10% (power 90%).

Data sources and statistical analysis

The intervention has been identified by The Municipality of Aarhus and the control group will be identified in the Danish Civil Registration System, as will parents and siblings to both intervention and control groups. Information on children's ethnicity, and demographic and socioeconomic status on parents will be obtained from Statistics Denmark. Data on HPVV 1 and 2 will be collected from The Danish National Health Service Register through the Danish Health Data Authority.

Demographic and socioeconomic characteristics will be presented as numbers and proportions and differences between intervention and control groups tested using Pearson's chi-squared test. Regression analyses will be used to estimate the relative risk of not being vaccinated between intervention and control group. If differences between intervention and control group are identified, both crude and adjusted estimates will be presented with 95% confidence intervals. All analyses will be performed using STATA V.17.

Ethical Considerations

The project will be conducted in accordance with the Good Clinical Practice Guidelines, and is reported to the Data Protection Agency in Central Denmark Region (ref.nr. 761330, 1-16-02-494-21) and Central Denmark Region's Committees on Biomedical Research (1-10-72-274-21). Parents must submit their child for vaccination via written informed consent. HPVV will be offered at pre-defined dates during school hours and provided by qualified medical professionals according to existing guidelines. Each HPVV will be registered in The National Danish Childhood Vaccination Register. All data will be handled according to the EU's General Data Protection Regulation and all sensitive information will be handled with 'e-boks', and REDcap. The municipality of Aarhus will provide personal data on intervention group in order to perform the invention and data processing agreement about disclosure has been concluded. Interviews will be executed in accordance with the Helsinki Declaration's rules on voluntariness and anonymity.

Research plan

[name] will be daily project manager and overall project leader. The PhD will follow the estimated timeline as shown in Figure 3, included already completed preparation scholarship.

Supervisors

[name] will be main supervisor, responsible for the qualitative methods and overall project. [name] will contribute as project leader as well as co-supervisor. [name] will be responsible clinician and co-supervisor. [name] will be responsible for the quantitative methods and co-supervisor.

Collaborators and user-representatives

From the Municipality of Aarhus, Department of Children and Youth, we have a consultant dedicated to the project. The project has been approved by Alderman [name], and [name], leader of the department, are close collaborator. Two school-nurses are user-representatives.

"Neighbourhood mothers" is a national volunteer organization of minority women trained in health, family and the Danish society. They constitute a large group of user-representatives. 10 mothers and children with various ethnic and social background are user-representatives, as well as 2 health professionals with cultural insight. "Sex og Samfund" has contributed with consultation regarding counselling material.

Perspectives

The perspectives of initiating school-based HPPV, is to create equal opportunities for participation in primary prevention from HPV-related cancer for all children living in DK. Results from this study may be used in future preventive interventions, and material can be used in future school-based vaccination programs.

We expect that the intervention will contribute to minimize misinformation and taboos related to HPVV among ethnic minority families, causing the intervention to indirectly benefit the HPVV attendance of the family's other children, and contribute to reduce inequality in health care.

This project is the first step in a larger project with an overall aim to improve HPV-related cervical cancer prevention among minority groups in DK, which takes place in a cross regional collaboration

FACULTY OF HEALTH SCIENCES

AARHUS UNIVERSITY

between Aarhus University Hospital, Odense University Hospital and Randers Regional Hospital (Figure 4).

Figures

Figure 1: Key elements in developing and evaluating complex interventions according to the Complex Interventions Framework (17).

[figure not shown]

Figure 2: quasi-experimental design.

[figure not shown]
[figure not shown]

Figure 3: Timeframe, PhD.

Months	1	2	3	4	5	6	7	8	9	10	11	12	13	14	15	16	17	18	19	20	21	22	23	24	25	26	27	28	29	30	31	32	33	34	35	36												
Years	1												2												3																							
Intervention	[Green bar]																																															
Schoolbased counselling	[Black bar]			[Green bar]																																												
School-based HPVV	[Black bar]			[Black bar]			[Black bar]			[Green bar]																																						
Implementation analysis	[Black bar]												[Green bar]																																			
Modelling process and outcomes	[Black bar]												[Black bar]						[Green bar]																													
Quantitative analysis	[Black bar]												[Green bar]																																			
Qualitative analysis	[Black bar]												[Green bar]												[Black bar]																							
Surveillance and monitoring	[Black bar]												[Green bar]																																			
Communication	[Green bar]																																															
Publications	[Black bar 1]												[Black bar 2]												[Black bar 3]																							
Presentations	[Grey bar]												[Grey bar]												[Grey bar]																							
Thesis	[Grey bar]																																	[Black bar Thesis]														
Phd related	[Green bar]																																															
Relevant Phd course attendance	[Grey bar]												[Grey bar]												[Grey bar]																							
Teaching	[Grey bar]												[Grey bar]												[Grey bar]																							
Exchange	[Grey bar]												[Grey bar]												[Grey bar]																							

Figure 4: Overview over patterns of attendance in HPVV and cervical cancer screening among Danish and minority women according to age as well as focus and age intervals in three studies. Study 1, which is the centre of this application, aims to improve HPVV coverage among minority children in Denmark (green box), study 2 aims to improve cervical cancer screening among young minority women in Denmark (blue box) and study3 aims to improve cervical cancer screening among older minority women in Denmark (orange box).

Tables

Table 1: Logic Model of intervention “School-based HPV-counselling and -vaccination”

RESSOURCES	ACTIVITIES/ PRODUCTS	CLIENTS	RESULTS		
			Short-term ”Attitude”	Intermediate ”Behavior”	Long-term ”Conditions”

Human Theory and development of intervention
 
 - Neighbourhood mothers - The municipality of Aarhus - School nurses - [name] 
Intervention
 
 - School nurses - School teachers - Vaccination staff - The municipality of Aarhus - Neighbourhood mothers 	
Parent counselling
 
 - Oral, 15 min. - Movie (oral performance) 
Pupils education
 
 - Movie (animation, facts) - In writing_(postcard) - Script for school nurses - Question cards 
Additional effort
 
 - letter with stamped envelope 
HPV-vaccination, first
 
 - Poster with short information (for parents, at school) - Script for vaccinators - Guideline for vaccination 
HPV-vaccination, second
 
 - Script for vaccinators - Guideline for vaccination 	
Pupils in fourth, fifth and sixth grade and their parents, at schools in the Municipality of Aarhus with 25% or more pupils with ethnical minority background.
	
Parents
 
 - Change of behavior (increased HPV-vaccinated pupils) - Awareness - Perception of relevance - Knowledge - Understanding - Motivation for screening 
Pupils
 
 - Change of behavior (increased HPV-vaccinated pupils) - Own provision - Knowledge - Understanding - Motivation - Positive interaction between students towards vaccination 	
Parents
 
 - Change of behavior (Women participate in screening) - Ambassadors and advice of HPV-vaccination in local environment - Decision about other children getting HPV-vaccinated 
Pupils
 
 - Positive influence of related children by positive mention of HPV-vaccination and prevention of disease by vaccination 	
Parents
 
 - Change in environmental tradition for HPV-vaccination - Less taboos related HPV and HPV-vaccination - Reduced fear of sexual behavior after HPV-vaccination due to change of focus - Change in culture about prevention of disease - Increased awareness about other cancer-preventing offers (breast, colon etc.) 
Pupils
 
 - Change in future behavior by increased attendance to both screening and vaccination of children in future generations. - Increased talk and awareness about HPV and HPV-vaccination. 
Society
 
 - Increased focus and interest regarding school-based vaccination

Assumptions and contextual factors

Environment

- **Anti-first-mover environment. Need for ambassadors locally.**
- **High trust to volunteers and health professionals (not GP's).**
- **High trust to school and school-nurses.**
- Positive mention by role-models and in media will benefit the outcome

Culture

- **Storytelling about preventing disease is more effective than focus on HPV being a sexual transmitted disease and best given before debut of sexual activity.**
- **Fear of change in sexual behavior after HPV-vaccination.**
- Broad presentation of ethnicities and authorities in project group and cooperators benefits the outcome of the project.
- Information pathway from child to parent

Intervention – form and materials

- **Minimal information about project will benefit the outcome → the less information and material, more manageable and larger participation to vaccination.**
- **The more uniform the intervention is, the stronger are our scientific methods.**
- **Nervousness among pupils must be taken into account. Minimal nervousness → more gets vaccinated.**
- Counselling of both parents and pupils will cause positive attitude to vaccination.
- Animation is the best platform for pupils
- Pupils want facts about HPV, cancer and vaccination.
- Pupils will have positive interaction between one another regards vaccination and counteract nervousness.
- We will not cluster and provoke anti-vaccination behavior by being progressive.

External Factors

- Eventual circumstances due to COVID-19 such as homeschool.
- Negative media attention of HPV
- Another project in the local community regarding vaccination (COVID-19), risk of double-nudging.
- Religious focus on sexual transmitted HPV-infection, and hereby increased fear of change in sexual behavior, possibly by senior religious figure.

Table 2: Schools and classes

No.	School	%-minority pupils	Participating classes	Total pupils
1	Ellehøjskolen	91%	5 th and 6 th grade	64
2	Møllevangskolen	46%	4 th , 5 th and 6 th grade	127
3	Skjoldhøjskolen	38%	4 th , 5 th and 6 th grade	130
4	Bakkegårdsskolen	30%	4 th , 5 th and 6 th grade	114
5	Sabro-Korsvejskolen	25%	4 th , 5 th and 6 th grade	201
	TOTAL	46% (Mean)		636

Table 3: Timeline of intervention

End of schooyear 2021/2022			Schooyear 2022/2023												
May	Jun	Jul	Aug	Sep	Oct	Nov	Dec	Jan	Feb	Mar	Apr	May	Jun		
			SCHOOL-BASED HPV-INTERVENTION												
First contact															
			Second contact												
			Parental counselling												
			Social media platform												
					Pupil education					Parental brush-up					
					HPVV1 2 weeks before: Aula 1 day before: Text					HPVV2 2 weeks before: Aula 1 day before: Text					
			Extra effort												

First contact	Via aula. "Offer to get HPV-vaccination during school-hours next schooyear. More information after the summer holidays".
Second contact	Via aula. "Offer to get HPV-vaccination durin school-hours this schooyear. More information at upcoming school-parental meeting" Included date for HPV1. Included link to exlusive social media page.
Parental counselling	School-parental meeting (local ambassadours present) Oral presentation and HPV-counselling by healthcare professional (10-15 min). Written material translated to minority languages. Possibility to give consent.
Social media platform	Exclusive for included parents. Coitaing brieft information. Film with parental counselling (1:1 as oral presentation). Link for consent.
Extra effort	E-boks and written letter with all written material included stamped return-envelope. Neighbourhood mothers as ambassabours in local community and at included schools.
Pupil education	In school hours by school nurse. Animation (3 min): facts about HPV and vaccination. Totebag with postcard. Schoolnurse: forum for sharing thoughts , experience with vaccination.
Parents brush-up	Brief update via aula. Included date for HPV2.
HPVV1	School-based vaccination by healthcare professionals. 2 weeks before: reminder at aula. Link to consent. 1 day before: reminder by text.
HPVV2	School-based vaccination by healthcare professionals. 2 weeks before: reminder at aula. Link to consent. 1 day before: reminder by text.

References

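### All intervention pupils come from five schools, but neither the power statement nor the planned regression allows for clustering by school, so the stated 90% power is too high and the confidence intervals have no specified basis

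*Combined protocol and SAP*

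**What the plan says.** Under Power calculation, the plan states "We have enrolled 5 schools, corresponding to approximately 640 children", with 2560 controls (1:4). It adds: "In both groups, roughly half of these children will be native Danes and the other half will be ethnic minorities". Taking 65% coverage in minority pupils, it concludes that "the study will be able to detect a difference of approximately 10 percent points in vaccination coverage" in the stratified analyses, with 5% type 1 error and 90% power. No ICC, design effect, cluster size or number of control clusters appears.

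The outcome is set out as: "Primary: HPVV coverage between intervention and control group as a total and stratified by ethnicity". For the analysis, Data sources and statistical analysis says "Regression analyses will be used to estimate the relative risk of not being vaccinated between intervention and control group", and that, if the groups differ, "both crude and adjusted estimates will be presented with 95% confidence intervals". No method that accounts for schools is named there or elsewhere. The plan does not say that default standard errors will be used; it leaves the matter open.

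Delivery is by school: a talk at the school's parent meeting, a session with the school nurse, and vaccination at school. Of the two doses it says: "Both will be given at pre-defined dates during school hours by qualified doctors and nurses". For controls, "the control group will be identified in the Danish Civil Registration System"; no school or area code for them is among the listed data.

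**The concern.** Pupils in one school share the same parent meeting, nurse, vaccination days and local opinion. The assumptions under Table 1 expect pupils to influence one another and local ambassadors to matter. Vaccination status within a school is therefore likely to be correlated, and 640 pupils in five schools carry less information than 640 independent pupils.

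Two things are at stake. The stated power would be too high. And if the regression were run with default standard errors, the 95% intervals would be too narrow, so a chance difference between five schools and the control areas could be read as an effect more often than 5% of the time. The total, minority and native analyses all rest on the same five schools. Ordinary cluster-robust standard errors with a normal reference do not solve this with so few treated clusters.

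**Working it through.** **Inputs.** From Power calculation: 320 versus 1280 pupils per stratum (half of 640 and 2560), 65% versus 75%, type 1 error 5%. Two-sided testing is assumed, as the plan does not say. From Table 2: school sizes and minority percentages. The ICC is assumed at 0.01, 0.02 and 0.05.

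**1. The plan's own figure, independent pupils.**
- Unpooled SE = √(0.75×0.25/320 + 0.65×0.35/1280) = 0.0276.
- Pooled proportion = (0.75 + 4×0.65)/5 = 0.67; pooled SE = √(0.67×0.33×(1/320 + 1/1280)) = 0.0294.
- Power, pooled: Φ((0.10 − 1.96×0.0294)/0.0276) = 93.8%. Unpooled: Φ(0.10/0.0276 − 1.96) = 95.1%.
- Difference detectable at 90% power: 9.3 points pooled, 9.0 unpooled, 9.6 with continuity correction, 9.9 for a fall from 65%.

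All of these round to about 10, so the stated figure fits independence.

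**2. With clustering, planned sizes.** Average cluster m = 320/5 = 64. Design effect DE = 1 + (m − 1)×ICC; effective n = n/DE. Each range covers the pooled and unpooled formulas.

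| ICC | DE | Power, intervention arm clustered | Power, both arms clustered | Detectable at 90% (both cases) |
|---|---|---|---|---|
| 0.01 | 1.63 | 80.6-84.4% | 77.3-80.9% | 10.8-11.8 points |
| 0.02 | 2.26 | 67.7-73.2% | 62.7-67.3% | 12.2-13.7 points |
| 0.05 | 4.15 | 42.9-49.9% | 37.9-42.7% | 15.3-18.1 points |

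Power is still 90% only up to an ICC of 0.0031 (pooled) or 0.0051 (unpooled) with the intervention arm clustered, and 0.0025 or 0.0039 with both arms clustered.

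**3. Stratum sizes implied by Table 2.** Table 2 gives percentages, not minority counts. Assuming each percentage applies to the participating pupils, the minority numbers are 58, 58, 49, 34 and 50 (sum 249; 250.5 unrounded), and the native numbers 6, 69, 81, 80 and 151 (sum 387). So 249/636 = 39%, not half. For 249 versus 996 or 1280 controls, power is 87-91% before any clustering. With m replaced by Σm²/Σm = 51.3, it is 70-79 / 57-68 / 35-47%. The first part of this shortfall comes from stratum size, not clustering.

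**4. Type 1 error if default standard errors were used.** With only the intervention arm clustered and 1:4 allocation, the variance of the difference is inflated by V = (DE + 0.25)/1.25, and the true size is 2×(1 − Φ(1.96/√V)).

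| Analysis | Σm²/Σm | ICC 0.01 | 0.02 | 0.05 |
|---|---|---|---|---|
| Minority | 51.3 | 9.8% | 14.5% | 25.9% |
| Native | 104.8 | 14.7% | 23.0% | 38.8% |
| Total | 142.3 | 17.9% | 27.8% | 44.7% |

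**5. Which corrections hold their level.** Beta-binomial simulation, 20,000 runs per setting: Table 2 sizes, 65% coverage, both arms clustered, controls in 10, 20 or 40 assumed equal areas, ICC 0 to 0.05. Type 1 error of a nominal 5% test:
- Ordinary cluster-robust, normal reference: 11.2-16.4%.
- Bias-reduced (CR2) cluster-robust on the log relative risk, Satterthwaite degrees of freedom (about 5): 3.5-5.8%. Adjusted for one binary covariate (5,000 runs per setting): 3.7-6.1%. With controls treated as unclustered, at most 7.5% (native, ICC 0.05).
- Random-intercept linear model, t with clusters minus 2: 2.3-6.1%.
- Unweighted cluster-level t-test, native stratum, 20 areas: 9.2 / 8.0 / 7.1% at ICC 0.01 / 0.02 / 0.05.

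The random-intercept and covariate-adjusted results each rest on one set of runs.

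**The case against.** The strongest reply is that the sizes above depend on things the plan does not state. It gives no ICC and does not commit to default standard errors, so the type 1 figures need both an assumed ICC and an assumed analysis. They also take the same ICC in every analysis and no reduction from covariate adjustment, although adjusted estimates are planned. That stands: the figures are scenarios. It does not rescue the 90%, which survives only at an ICC close to zero, and an unspecified method can still be chosen after the data are seen.

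Second, the match to independence is loose: at exactly 65% versus 75% the calculation gives 94-95%, not 90%. True. The fit is to the rounded detectable difference and does not prove how the figure was obtained. The slack covers only the very small ICCs shown above.

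Third, area information is probably available. Controls are to come from comparable regions, and the sibling comparison is to be area matched. This lowers the cost of the fix, but the plan does not say that the area will be used in the analysis.

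Fourth, the schools are already enrolled and were not randomised. Restating power changes no sample size, and no cluster correction removes bias from the way schools were chosen. Both points are right; neither makes the intervals correct for clustering.

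**Conclusion.** The concern holds and should be fixed before analysis. What the documents establish is that five schools supply all intervention pupils, that the power statement has no allowance for clustering, and that no cluster-aware analysis is specified. The 90% at about 10 points is too high for this design unless the ICC is below about 0.0025-0.005; at ICCs of 0.01-0.05, power at the planned sizes is between 84% and 38%. The error rate of the planned regression cannot be known because the method is not stated; with default standard errors it would be well above 5% in all three primary analyses. These sizes rest on an assumed ICC range, two-sided testing and, for the stratum sizes, the Table 2 percentages applying to participating pupils.

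**What to change.** 1. Replace the unqualified 90% with power, or detectable difference, over a stated ICC range, using actual minority counts or, failing those, the counts implied by Table 2.
2. Keep the school identifier for intervention pupils, obtain a school or residential-area code for controls with the register data, and state the number of control clusters.
3. Prespecify one cluster-aware analysis with a small-sample correction that yields the planned crude and adjusted relative risks. One tested option is Poisson regression with log link, CR2 standard errors and Satterthwaite degrees of freedom. The random-intercept linear model has more power, but it was not tested with covariates and assumes equal ICC in both arms, so it fits better as a sensitivity analysis. Do not rely on ordinary cluster-robust errors with a normal reference, or on an unweighted cluster-level t-test in every stratum.
4. Repeat the simulation with the real control areas and covariates before use, and confirm that the planned software can run the method.

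**Cost.** One area code, a short simulation, wider intervals and a plainly lower power statement. For the Table 2 minority counts, 65% versus 75%, and 10 to 40 assumed control areas, simulated power at ICC 0.01 / 0.02 / 0.05 is about 44-48 / 32-37 / 18-23% with CR2 (65% at ICC 0) and 61-71 / 48-59 / 28-38% with the random-intercept model (81-84% at ICC 0). A second simulation of CR2 with 20 areas gave 50 / 39 / 24%, against 46 / 36 / 21% in the main runs, so these are good to a few points only. The change corrects the intervals for clustering; confounding between the chosen schools and the control areas remains a separate matter.
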